CharitéCentrum für Audiologie / Phoniatrie, Augen und HNO-Heilkunde

TRIAL PROTOCOL

Sponsor

Charité – University Medicine Berlin
[name]
[name]
Germany

Principal Coordinating Investigator (PCI):

[name]. [name]
Charité, University Medicine Berlin
Department of Ophthalmology, CBF
[name]
[name]
Germany

Trial protocol code: **DORO001**

Trial title: **Influence of diabetes control on treatment of
diabetic macular edema with ranibizumab**

DRKS: 00004731

EudraCT number: 2012-003943-32

Version of 23 July 2015, Version Final

The information in this trial protocol is strictly confidential. It is for the use of the sponsor, investigator, trial personnel, ethics committee, the authorities, and trial subjects only. This trial protocol may not be passed on to third parties without the express agreement of the sponsor or the Principal Coordinating Investigator (PCI, "Leiter der klinischen Prüfung (LKP)").

Signatures

Protocol authorization signature page

Trial code: DORO001

Title: Influence of diabetes control on treatment of diabetic macular edema with Ranibizumab

EudraCT-No: 2012-003943-32

Approved by the following

[name]. med. [name]
(Principal Coordinating Investigator, PCI)
Charité, Department of Ophthalmology, Berlin;
Acting on behalf of the sponsor

Signature

Date

Signature

[figure not shown]
Date

Signature

Date

I. Synopsis

Sponsor:	Charité, University Medicine Berlin [name] [name] Germany Represented by: [name]. med. [name] Charité University Medicine Berlin Department of Ophthalmology, CBF [name] [name] Germany
Principal Coordinating Investigator:	[name]. med. [name]
Title of the clinical trial:	Influence of diabetes control on treatment of diabetic macular edema with ranibizumab
Indication:	Diabetic Macular Edema
Phase:	IV, therapeutic-exploratory trial
Type of trial, trial design, methodology:	Monocentre, two-arm, randomised, parallel-group controlled clinical trial in Germany
Number of subjects:	60 patients per treatment arm (total 120)
Primary trial objective:	To evaluate the influence of an intensified diabetes control programme on treatment of diabetic macular edema with ranibizumab.
Study endpoints:	Primary endpoint: 
• Change of best corrected visual acuity in ETDRS letters score at month 12 when compared with baseline (measured by the difference in ETDRS letters score between month 12 and baseline) Secondary endpoints: 
• Number of treatments with ranibizumab up to 6, 12, 18 and 24 months of treatment respectively• Mean average change in BCVA at 6, 12, 18 and 24 months after initial treatment• Macular thickness (as measured with OCT) at 6, 12, 18 and 24 months after initial treatment• Time to reach target HbA1c• Number of neovascular complications: need for panretinal laser photocoagulation (PRP)• Rates of ocular and of systemic AEs (retinal detachment, central retinal artery occlusion, endophthalmitis; rates of stroke, myocardial infarction, severe hypoglycemia)

Medical condition:	Diabetic patients with visual impairment due to diabetic macular edema (DME)								
Principal inclusion criteria:	
 • Patients with diabetic macular edema relevant to visual acuity • OCT central retinal thickness $\geq 250\mu\text{m}$ • HbA1c $> 6,5\%$ at initial visit • BCVA ≤ 0.8 and ≥ 0.05 • Age ≥ 18 years • Written patient informed consent given 								
Principal exclusion criteria:	
 • Previous treatment with intravitreal drugs in last 6 months • Vitreous hemorrhage as a consequence of proliferative retinopathy • Pregnancy • Blood pressure of $\geq 180/100$ (or uncontrolled pressures under pharmacological therapy) • Chronic systemic or ocular inflammatory/autoimmune diseases (e.g. inflammatory bowel disease, Addison's disease, Cushing Syndrome, Uveitis) • Systemic cortisone or anti-VEGF therapy • Acute systemic or ocular infectious diseases 								
Name of investigational medicinal product (IMP):	Ranibizumab (Lucentis®)								
Investigational medicinal product – dosage and method of administration:	Ranibizumab – three initial monthly intravitreal injections (0.05 mg) and subsequent injections until visual acuity reached maximum (maximum of visual acuity defined as stable visual acuity under treatment with ranibizumab on three consecutive monthly control visits)								
IMP or therapy used as a comparator – dosage and method of administration:	not applicable								
Duration of treatment:	12 months treatment period with Ranibizumab Total follow-up is 12 months (with PRN treatment option)								
Time plan:	
 
 First patient first visit (FPFV):	01 August 2015	
 
 Last patient first visit (LPFV):	31 May 2018	
 
 Last patient last visit (LPLV):	31 May 2020	
 
 Final study report:	31 April 2021	
 
	First patient first visit (FPFV):	01 August 2015	Last patient first visit (LPFV):	31 May 2018	Last patient last visit (LPLV):	31 May 2020	Final study report:	31 April 2021
First patient first visit (FPFV):	01 August 2015								
Last patient first visit (LPFV):	31 May 2018								
Last patient last visit (LPLV):	31 May 2020								
Final study report:	31 April 2021								
Statistician:									

- Statistical methods:** For the comparison of means between two arms ANCOVA is used (normality assumption is assessed graphically and if necessary, will be tested by Shapiro-Wilk statistic. If the normality assumption is violated a nonparametric test is applied).
Repeated measurement analysis for BCVA and central retinal thickness.
Log-rank test and Cox model for time to reach target HbA1c
Chisquare test for the number of neovascular complications and AE comparisons if applicable, otherwise the Fishers exact test will be performed.
Descriptive statistics in terms of mean, standard deviation (SD), median, 25th and 75th percentiles, 95% confidence Intervals and frequency tables.
- GCP conformance:** The present trial will be conducted in accordance with the valid versions of the trial protocol, ICH Good Clinical Practice Guidelines (ICH-GCP) and applicable local regulatory requirements.
- Financing:** This investigator initiated trial is financially supported by Novartis Pharma, Nürnberg, Germany. Trial Sponsorship is taken over by Charité University Medicine Berlin.

Table of contents

Signatures	2
I. Synopsis	3
List of tables	8
List of figures	8
II. Abbreviations	9
1. Introduction	10
2. Objectives of the clinical trial	11
2.1. Rationale for the clinical trial	11
2.2. Primary objective / Hypothesis:	11
2.3. Secondary and other objectives	11
3. Rates of organisational and administrative aspects of the trial	12
3.1. Sponsor	12
3.2. Principal Coordinating Investigator	12
3.3. Statistics	12
3.4. Data Monitoring Committee	12
3.5. Further committees	12
3.5.1. Steering Committee	12
3.5.2. Advisory Committee	12
3.5.3. Imaging Review Board	12
3.6. Study laboratories and other technical services	13
3.7. Central organisation units	13

Diabetic macular edema (DME) is the leading cause of blindness in young adults in developed countries, affecting 12 % of type 1 and 28% of type 2 diabetic patients (Kiire et al. 2013). The gold standard DME treatment should be based on a good control of glycemia along with control of lipids and hypertension function. However, despite the systemic metabolic control values being essential for patients with diabetic retinopathy, it has proven to be insufficient for DME if it appears. With these patients, additional measures are needed in order to avoid the subsequent loss of vision. The introduction of intravitreal corticosteroids or anti-VEGF drugs have shown their safety and efficacy and together with laser photocoagulation are currently the treatments of choice in the management of DME (Boyer et al. 2014; Ip et al. 2015).

The management of systemic risk factors, such as hyperglycemia and arterial hypertension, remains a task of great importance despite all modifications and increase of knowledge during recent years.

The current study intends to investigate the effect of optimized glycemic control (HbA1c < 6,5% if possible without side-effects; triglycerides < 140 mg/dl; RR < 140/90 mmHg) on diabetic macular edema and the number of treatments required.

VEGF (Vascular Endothelial Growth Factor), an angiogenic stimulating factor plays an important role in neovascularization of the retina and vascular leakage leading to macular edema (Ferrara et al. 1997; Kijlstra et al. 2005). Drugs that inhibit VEGF are therefore being investigated for their therapeutic potential (Chang et al. 2007; Edelmann et al. 2005).

Ranibizumab (Lucentis®) is a recombinant humanized IgG1 κ isotype monoclonal antibody fragment that binds to human VEGF and prevents interaction with its receptors VEGFR1 and VEGFR2 on the surface of endothelial cells, thereby reducing endothelial cell proliferation, vascular leakage and the formation of new blood vessels (Chen 1999, Gaudreault 2005).

Ranibizumab is designed for intraocular use and approved in USA and Europe for the treatment of age-related macular degeneration (AMD), visual impairment due to diabetic macular edema (DME), macular edema due to retinal vein occlusion (RVO), and choroidal neovascularization in pathologic myopia (Michels et al. 2005; Rosenfeld et al. 2006). The overall safety profile of ranibizumab, both ocular and non-ocular, was demonstrated to be favorable in many studies with wet AMD, DME and RVO.

The aim of this prospective randomized study is to investigate whether a intensified diabetic control program leads to better final visual acuity and less frequent diabetic ocular complications in patients with diabetic retinopathy when compared with a normal diabetic treatment.

2. Objectives of the clinical trial

2.1. Rationale for the clinical trial

Several studies showed the significant reduction of DME after ranibizumab injections (Do et al. 2012, DRCR Network 2012). Patients could significantly increase their visual acuity under treatment and the safety profile is favourable compared to the application of intravitreal steroids. However, the treatment burden remains high, as ideally patients would receive monthly ranibizumab injections. This still provides a challenge for health care providers and patients alike.

Published studies showed that the intensive insulin treatment and diabetic control can reduce the risk of most retinopathy-related complications (Maple-Brown et al. 2012; Zhang X et al. 2014). However the most recently published meta-analysis could not confirm the reduction of prevalence of vision loss or blindness (Zhang X et al. 2014). Therefore further studies are needed to investigate the effect of intensive diabetic control on visual acuity. Our study is based on the hypothesis that an intensive insulin treatment will positively affect the visual acuity in patients with DME and reduce the need for re-treatment.

2.2. Primary objective / Hypothesis:

The trial investigates the influence of an intensified diabetes control programme on treatment of DME.

As a primary objective the change of best corrected visual acuity in ETDRS letters score at month 12 when compared with baseline (measured by the difference in ETDRS letters score between month 12 and baseline) will be evaluated.

2.3. Secondary and other objectives

The secondary objectives of the trial are:

- To evaluate the number of treatments with ranibizumab up to 6, 12, 18 and 24 months of treatment respectively
- To evaluate the mean average change in BCVA at 6, 12, 18 and 24 months after initial treatment
- To evaluate the macular thickness (as measured with OCT) at 6, 12, 18 and 24 months after initial treatment
- To evaluate the time needed to reach the target HbA_{1c}
- To evaluate the number of neovascular complications with need of PRP
- To evaluate the safety of the treatment of DME with ranibizumab based on ocular (e.g. retinal detachment, central retinal artery occlusion, endophthalmitis) and systemic AEs (e.g. rates of stroke, myocardial infarction, severe hypoglycemia)

3. Rates of organisational and administrative aspects of the trial

3.4. Data Monitoring Committee

There will be no Data Monitoring Committee set up in this clinical trial.

3.5. Further committees

3.5.1. Steering Committee

There will be no Steering Committee set up in this clinical trial.

3.5.2. Advisory Committee

There will be no Advisory Committee set up in this clinical trial.

3.5.3. Imaging Review Board

Best corrected visual acuity (BCVA), size of areas of macular and peripheral capillary drop-out, macular thickness will be analyzed in a blinded fashion by experienced and certified image graders that are part of the study team at the Charité.

3.6. Study laboratories and other technical services

All laboratory assessments will be performed by the central laboratory of Charité University Medicine Berlin.

There are no other technical service tasks that will be performed by other service providers.

3.8. Investigators and trial sites

This clinical trial will be carried out as a monocentric trial at the Charité department of ophthalmology (Campus Benjamin Franklin) in collaboration with the department of diabetology, endocrinology and nutritional medicine (Campus Benjamin Franklin) in Berlin, Germany.

Requirements for investigators and trial sites

The investigators and involved physicians at the department of ophthalmology should be familiar with intravitreal injection procedures as well as macular laser. The investigators and trial site staff have to proof knowledge of regulatory procedures, GCP and experience with the conduct of the clinical testing of pharmaceutical preparations. The investigators and involved physicians are required to have special experience in the indication of DME.

3.9. Financing

This investigator initiated trial is financially supported by Novartis Pharma, Nürnberg, Germany. Trial sponsorship is taken over by Charité University Medicine Berlin.

4. Trial conduct

4.1. General aspects of trial design

This is a monocentre, phase IV, two-arm, randomised, parallel-group, controlled clinical trial.

4.1.1. Time plan

[figure not shown]
Table 1: Time plan of the trial

First patient first visit (FPFV):	01 August 2015
Last patient first visit (LPFV):	31 May 2018
Last patient last visit (LPLV):	31 May 2020
Final study report:	31 April 2021

End of the clinical trial

The end of the trial is defined as the last visit of the last patient included (LPLV).

Figure 1: Trial flowchart

4.2. Discussion of trial design, randomization and study arms

Selection bias is minimised by concealed random assignment of trial arms. Observer-masking (assessment of BCVA, macular thickness, capillary drop-out) is done to guard against *detection bias*. *Performance bias* is to be reduced by strict standardisation of trial procedures. *Attrition bias*

will be minimised by active follow-up of trial patients by a dedicated study nurse / physician (telephone, mail and in-person contact).

Randomisation of patients into two treatment arms will be performed centrally by CROLLL GmbH and will be computer-assisted, based on block-randomization lists. A randomization ratio of 1:1 will be used. No stratification is planned.

Patients will be randomized to one of the two study arms:

1. Regular Glycemic Control (Group 1): patients randomized into this group will be controlled by their general practitioner or private diabetologist (usual care). The glycemic control (blood measurements of HbA1c) will be performed at trial site (Department of diabetology, endocrinology and nutritional medicine) every 3 months. The site will not influence or change the diabetes medication given by general physician and serves as an observer only to monitor the diabetic control.
2. Intensified Glycemic Control (Group 2): patients randomized into this group will be controlled at the trial site (Department of diabetology, endocrinology and nutritional medicine) during first year monthly, in the second study year every 3 months. The individual HbA1c will be targeted according to the general status reflecting other risk factors for the vasculopathy (e.g. BMI, smoking, blood pressure, lipid status). All effort will be done to reach the target blood pressure $\leq 140/90$ mmHg and blood triglyceride level < 140 mg/dl: Further the patients will be educated to improve their eating habits in regard to reduce the carbohydrate intake.

4.3. Selection of trial population

Reasons for gender distribution

We expect a homogenous (1:1) gender distribution. There is no evidence of difference by gender in the incidence of DME or in the response to anti-VEGF agents.

4.3.1. Inclusion criteria

1. Patients with diabetic macular edema relevant to visual acuity
2. OCT central retinal thickness $\geq 250\mu\text{m}$
3. HbA1c $> 6,5\%$ at initial visit
4. BCVA ≤ 0.8 and $\geq 0,05$
5. Age ≥ 18 years
6. Written informed consent given

4.3.2. Exclusion criteria

1. Participation in other interventional trials
2. Previous treatment with intravitreal drugs in last 6 months
3. Vitreous hemorrhage as a consequence of proliferative retinopathy which would hamper adequate diagnosis and imaging
4. Blood pressures of $\geq 180/100$ (or uncontrolled pressures under pharmacological therapy)
5. Chronic systemic or ocular inflammatory/autoimmune diseases (e.g. inflammatory bowel disease, Addison's disease, Cushing Syndrome, Uveitis) which would influence the trial's outcome (at the physician's discretion)
6. Systemic cortisone or anti-VEGF therapy
7. Acute systemic or ocular infectious diseases
8. Prior laser photocoagulation treatment within 3 months (focal / grid laser or panretinal) prior to study entry
9. Contraindications as stated in summary of medicinal product characteristics or Investigator's Brochure of Ranibizumab
10. Current treatment with pharmaceutical preparations with which interactions can be expected
11. Diseases or findings that may have a significant effect on the target variables and which may therefore mask or inhibit the therapeutic effect under investigation at the investigator's discretion
12. Persons who have a fluorescein allergy
13. Women who are pregnant or breast feeding (pregnancy defined as the state of a female after conception and until the termination of gestation), confirmed by a positive hCG urine test at screening
14. Women who are menstruating and capable of becoming pregnant* and not practicing a medically approved method of contraception (Pearl Index $<1^{**}$) during and up to at least 12 weeks after the end of treatment. A negative pregnancy test (urine) for all women is required with sufficient lead time before inclusion

*definition of post-menopausal: 12 months of natural (spontaneous), amenorrhea or 6 months of spontaneous amenorrhea with serum FSH levels >40 mIU/ml or 6 weeks post surgical bilateral oophorectomy with or without hysterectomy

**examples of particularly reliable methods with Pearl Index (PI) <1 , according to guidelines of Deutsche Gesellschaft für Gynäkologie und Geburtshilfe:

- Combination pill with estrogen and gestagen (no mini-pill, PI=0.1-0.9)
- Vaginal ring (NuvaRing®, PI=0.65 uncorr.; 0.4 corr.)
- Contraceptive patch (EVRA®, PI= 0.72 uncorr.; 0.9 corr.)
- Estrogen-free ovulation inhibitors (Cerazette®, PI=0.14)
- Progestin-containing contraceptives (Implanon®, PI=0-0.08)
- Injectable 3-month depot progestins (PI=0.3-1.4; 0.88 corr.)
- Intra-uterine progesterone device (Mirena®, PI=0.16)

15. Persons with any kind of dependency on the investigator or employed by the sponsor or investigator
16. Persons held in an institution by legal or official order or legally incapacitated

4.4. Withdrawal of trial subjects after trial start

Study subjects will be early discontinued from participation in the study if

- they withdraw consent from participating in the study
- no response to the ranibizumab treatment is observed, defined as persisting macular edema without any reduction of central retinal thickness after 3 consecutive monthly injections
- they present visual loss defined as ≥ 30 ETDRS Letters when compared with the baseline
- they develop vitreous bleeding due to active neovascularisation of the retina or optic disc confirmed by fluorescein angiography with need of surgical treatment (vitrectomy)
- any other clinical adverse event (AE), laboratory abnormality, illness or other medical condition or situation occurs that would not go along with the best interest of the patient in case of continuing the participation.

Note: Each patient should be followed-up even if the study treatment is discontinued.

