4.4.1. Procedures for premature withdrawal from treatment during the trial

In case of patient withdrawal during the study period all data collected until this point of time will be stored according to AMG §40, 2a, 3. The patient must not be replaced.

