4.5.2. Premature termination of trial

The sponsor has the right to terminate the trial prematurely if there are any relevant medical or ethical concerns or if completing the trial is no longer practicable. If such action is taken, the reasons for terminating the trial must be documented in detail. All trial subjects still under treatment at the time of termination must undergo a final examination which must be documented. The PCI must be informed without delay if any investigator has ethical concerns about continuation of the trial.

The trial must be terminated if:

- The risk-benefit balance for the trial subject changes markedly
- It is no longer ethical to continue treatment with the IMP
- The sponsor considers that the trial must be discontinued for safety reasons
- It is no longer practicable to complete the trial, e.g. due to scientific reasons

PCI decides on whether to discontinue the trial based on medical data and/or in consultation with the statistician.

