4.6.1. Treatments to be given

In all patients (in both study arms) the diabetic macular edema will be treated with intravitreally given ranibizumab.

Dosage and administration of Ranibizumab

Injections are administered according to the current summary of product characteristics Lucentis®, i.e. monthly until maximum BCVA can be observed:

Starting at visit 1, ranibizumab will be administered intravitreally in a multiple-dose regimen of 0.5 mg of ranibizumab every month for a total of 3 injections and as a PRN treatment thereafter (subsequent injections until maximum BCVA is observed).

Injection is discontinued when

- no BCVA improvement in spite of treatment is seen after the first three injections (i.e. after three consecutive monthly visits)

BCVA assessments will take place monthly. Monthly injections are resumed when

- decrease in BCVA due to worsening of DME in the opinion of the investigator is observed

Injections are continued until BCVA improvement is seen after three consecutive monthly visits.

If a subject is unable to receive study drug because of medical or personal reasons, treatment should be resumed within 2 weeks of the scheduled treatment. If a subject is unable to receive study drug within 2 weeks of the scheduled treatment, the subject will be allowed to miss the scheduled dose and resume treatment at the next regularly scheduled time. Dosing should not occur more frequently than every 4 weeks. Missed doses will not be replaced.

Ranibizumab Injection

Procedures will be implemented to minimise the risk of potential adverse events associated with serial intraocular injections (e.g., endophthalmitis). Aseptic technique must be observed by clinic staff involved in the injection tray assembly, anesthetic preparation and administration, and study drug preparation and administration. In addition to the procedures outlined in the protocol, added safety measures in adherence to specific institutional policies associated with intraocular injections should be observed.

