4.6.8.1. Rescue therapy for emergencies

Rescue medication allowed in this study is panretinal and/or focal laser treatment (after 3 consecutive monthly injections) and only if a significant progression of neovascularization with associated threat of visual loss is seen. Laser treatment will be documented on the appropriate trial database/CRF pages.

The ranibizumab injection can be performed at the same day as a laser therapy, but not earlier than 30 minutes after laser treatment.

If the therapeutic effect will be considered insufficient by either the patient or the treating physician the patient may be withdrawn from the study and is able to receive whatever treatment is considered to be necessary.

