4.6.9. Continuation of treatment after the end of the clinical trial

The investigator must provide follow-up medical care for all patients who are prematurely withdrawn from the study, or must refer them for appropriate ongoing care.

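### Section 4.4 ends study participation, not only ranibizumab, for three eye-failure events, and its follow-up note does not say which visits continue

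*Combined protocol and SAP*

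**What the plan says.** Section 4.2 randomises patients to regular or intensified glycaemic control. Section 4.6.1 gives the eye treatment to everyone: "In all patients (in both study arms) the diabetic macular edema will be treated with intravitreally given ranibizumab".

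Section 4.4 opens its list with "Study subjects will be early discontinued from participation in the study if". The list contains withdrawal of consent, three eye events (no reduction in central retinal thickness after three monthly injections, loss of at least 30 ETDRS letters from baseline, vitreous bleeding that needs vitrectomy) and a general clause on the patient's best interest. Under the list stands: "Note: Each patient should be followed-up even if the study treatment is discontinued". Section 4.6.8.1 adds an option for insufficient effect: "the patient may be withdrawn from the study and is able to receive whatever treatment is considered to be necessary".

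Four other places bear on what happens next:

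- 4.4.1: "In case of patient withdrawal during the study period all data collected until this point of time will be stored". It also rules out replacement.
- 4.6.9: "The investigator must provide follow-up medical care for all patients who are prematurely withdrawn from the study", or must refer them elsewhere.
- 4.5.2: "All trial subjects still under treatment at the time of termination must undergo a final examination which must be documented". This applies only if the whole trial is stopped early.
- 4.2: attrition bias "will be minimised by active follow-up of trial patients by a dedicated study nurse / physician", by telephone, mail or in person.

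**The concern.** Failure of the eye treatment can be a good reason to stop injecting. It is not in itself a reason to stop observing a patient whose randomised assignment is a diabetes programme. Such a patient can usually still attend the diabetes, BCVA and OCT visits.

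The lead sentence nevertheless removes the patient from the study, and it is worded as mandatory. The note is worded as a recommendation and presupposes that only treatment has stopped. Treatment is open-label (4.6.7), so staff who know the arm could read the section differently from one patient to the next. At stake are the month-12 and later outcomes of the patients whose eyes do worst. Once missed, those measurements cannot be recovered at the analysis stage.

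**Working it through.** **1. Are the triggers related to the outcomes?** Setting 4.4 beside 4.7.1:

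| Trigger in 4.4 | Related endpoint |
|---|---|
| No thickness reduction after 3 injections | OCT macular thickness (secondary) |
| Loss of 30 or more letters | ETDRS change from baseline (primary scale) |
| Neovascular bleeding needing vitrectomy | Neovascular complications, counted as need for PRP (secondary; related, not identical) |

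All three are, so exit under the lead sentence is not independent of outcome.

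**2. Does any section set outcome visits after such an exit?** Section 4.4.1 covers data storage and non-replacement, 4.6.9 medical care, 4.5.2 termination of the trial, and 4.2 general contact. Tables 2 and 3 contain no early-termination visit and no rule for discontinued patients. The note in 4.4 names no visit, assessment or duration.

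**3. What would a thickness non-responder miss?** Inputs are from Tables 2 and 3: BCVA and OCT are scheduled at each of visits 1 to 24, and the first three injections fall at visits 1, 2 and 3. The first OCT after the third injection is at visit 4. If the patient leaves there:

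- rest of Table 2: 12 − 4 = 8 visits
- all of Table 3: 24 − 12 = 12 visits
- total missed: 8 + 12 = 20 of 24 (83%)

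The missed visits include month 12 and all four secondary time points (6, 12, 18 and 24).

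**4. What does the analysis then do?**

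- *Exit with a score at least 3 months in:* 6.1.3 uses the closest such score, so an earlier value stands in for month 12.
- *Exit before 3 months* (possible for the letter-loss and bleeding triggers): there is no eligible score, and 6.1.8 imputes nothing unless stated otherwise. The patient is in the ITT set of 6.1.1 but has no primary outcome.
- *Exit at visit 4:* this is 4 − 1 = 3 monthly intervals after the first injection, though Table 2 labels it month 4. Given the one-week window, eligibility depends on how months are counted.
- *Secondary BCVA and thickness:* LOCF under 6.1.4 carries the last value forward. For an exit at visit 4, one value fills all four time points.
- *HbA1c and PRP* after exit are not collected, although both feed secondary endpoints.

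If the note is followed instead, the real values exist and none of this arises.

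**5. Can the effect be sized?** The plan's sample size reproduces: 2.0/3.5 = 0.571, and a two-sided 5% t test with 56 per arm has power 0.850. Randomising 60 leaves 60 − 56 = 4 per arm (4/60 = 6.7%) for drop-out. The documents give no rate for any trigger and no expected difference between arms, so neither the share of that allowance used up nor a bias in letters can be derived.

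**The case against.** The strongest reply is that follow-up is already intended. The note sits directly under the list and covers every patient, the heading of 4.4.1 refers to withdrawal from treatment, 4.2 aims to limit attrition, and the ITT definition allows no exclusions. Tables 2 and 3 schedule BCVA and OCT whether or not an injection is given. Section 4.6.1 stops injections when acuity does not improve after the first three, yet keeps monthly acuity assessments. On this view 4.4 is loosely worded and needs only clarifying.

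Much of that stands. A reader might infer that the protocol sets out to drop these patients; the note does not support so strong a reading. But the lead sentence says the opposite of the intended reading, and the tables apply to participants, which is the status that sentence removes. The contrast with 4.6.1 also shows that stopping the drug while continuing to observe is already workable in this trial.

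Two further points are fair. Vitreous haemorrhage can prevent useful imaging, as exclusion criterion 3 recognises, so not every missing value is avoidable. And a protocol may choose not to measure vision under a different eye treatment: the title concerns treatment with ranibizumab, and 4.6.8 classes vitrectomy as treatment failure. That is a legitimate choice, but it should be made explicitly, and it would not justify losing the HbA1c and PRP data.

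**Conclusion.** The point holds as an ambiguity with a real consequence. One reading of 4.4 causes outcome-dependent and largely avoidable loss of month-12 and later data; the other does not, and the protocol does not say which applies. The firm figure is 20 of 24 BCVA and OCT visits lost for a non-responder removed at visit 4. It assumes that removal follows the first OCT after the third injection.

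Two stronger conclusions are tempting but unsupported. The first is that the primary comparison will be biased by some amount or towards one arm. Without trigger rates, size and direction are unknown, and there is no shift if both arms lose equal numbers with equal gaps between substituted and true scores. The second is that power will be lost. The closest-score rule keeps later exits in the analysis with a substituted value; only exits without an eligible score reduce the numbers.

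This is a change the sponsor should make because it is cheap and the missed data cannot be recovered. It is not a demonstrated failure of the primary analysis.

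**What to change.** - **4.4 and 4.6.8.1:** list the three eye events, and insufficient effect, as reasons to stop ranibizumab. Keep withdrawal of consent and the patient's best interest as reasons to leave the study.
- **Note in 4.4:** replace it with: *A patient who stops ranibizumab for these reasons stays in the assigned diabetes arm and in the Table 2/3 visits (at least BCVA, OCT, HbA1c and PRP, where assessable, including months 12 and 24) unless consent is withdrawn.*
- **4.6.8:** allow other eye treatment or vitrectomy once ranibizumab has been stopped, and record its date and type. It can still count as treatment failure.
- **6.1.6:** add a sensitivity analysis of the primary endpoint that uses the last score before the other treatment. The primary analysis rule needs no change, since 6.1.3 already uses the month-12 score when there is one.

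The adverse-event window, which 7.1.1 ties to the end of ranibizumab, affects anyone who stops injections and is a separate matter.

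Cost: an amendment under section 9, with written reasons, the authors' signatures and, where required, ethics committee and authority approval. Lifting the 4.6.8 restriction for these patients is a change of substance, not only of wording. No visits are added. The main downside is that some month-12 scores will reflect other eye treatment, which the sensitivity analysis addresses.
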